9.1 Operating Characteristics

The operating characteristics and associated power are estimated for different dose-response scenarios by computer simulations using the Fixed and Adaptive Clinical Trial Simulator (FACTS) version 5.6. The five sigmoidal dose-response profiles that were used to simulate trial data are illustrated in Figure 9-1. Further details on the dose-response model and the associated primary analysis are given in Section 9.7.2 and Appendix 2.

[figure not shown]

Figure 9-1 Dose-Response Scenarios

The longitudinal data profile used in the simulations is based on pooled data from desmopressin clinical trials FE 992026 CS40 and FE 992026 CS41 (planned treatment group). The following estimates and assumptions were used:

- Dose-response standard deviation $\sigma = 0.95$ voids
- A between to total variance (σ^2) ratio of 0.90 and a true underlying σ of 0.95
- Response fractions of 0.8142, 0.9328 and 0.9874 at Weeks 1, 4 and 8, respectively, as compared to the averaged dose-response at Week 12
- Variance fractions of 0.8481, 0.8329 and 0.8900 at Weeks 1, 4 and 8, respectively, as compared to the averaged dose-response at Week 12

Further design specifications were:

- During the initial 17 weeks the recruitment rate will increase linearly from 0 to 8.2 subjects per week
- After 17 weeks, when all trial sites have been initiated, the recruitment rate is assumed to remain constant at 8.2 subjects per week
- Constant dropout rate of 15% during the randomised treatment period
- First interim analysis when 125 subjects are randomised, thereafter interim analyses every 8 weeks
- Up to the first interim analysis the allocation ratio is 2:2:1 for placebo, 500 μg FE 201836 and desmopressin
- After the first interim analysis the allocation ratios are 2:7:1, for placebo, 50-500 μg FE 201836 and desmopressin
 - Subjects randomised to FE 201836 will be dynamically allotted to 50 μg FE 201836, 100 μg FE 201836, 150 μg FE 201836, 250 μg FE 201836, 350 μg FE 201836 or 500 μg FE 201836 using response-adaptive allocation as outlined in Section 9.11.
- Maximum of 300 randomised subjects

These settings were shared for all treatment groups. The average number of subjects and probabilities for futility and success are presented in [Table 9-1](#).

Table 9-1 Operating Characteristics

Dose-Response Scenario	Maximum response (α_2)	ED ₅₀ (α_3)	Average Number of Subjects	Futility Stopping at First Interim	Total Futility stopping	Power (Total Success)

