The imputed final response (visit T) for the i th subject is modeled as:

$$Y_i \sim \mu_d + \delta_i + N(0, \lambda_T^2)$$

that is, with γ_T equal to 0. Thus, the model has components for

- the per subject difference in response (δ_i) from the mean dose response (μ_d),
- the error as a function of knowing the i th value is modeled, $N(0, \lambda_T^2)$

The prior distributions are:

$$\gamma_t \sim N(\mu_\gamma, \sigma_\gamma^2)$$

$$\delta_i \sim N(0, \tau_i^2)$$

$$\tau_i^2 \sim IG(a_\tau, b_\tau)$$

$$\lambda_t^2 \sim IG(a_\lambda, b_\lambda)$$

We define 3 separate model instance for correlating the averages observed at earlier visits to the final primary endpoint value. The control, active comparator, and 6 active doses of FE 201836 are modeled with separate model instances. Each model instance will be fit using only the data from the arm(s) it corresponds to. All model instances are identical and we use the same priors for all instances. The priors are

Trial Code: 000233

$$\tau_f^2 \sim IG(0.5, 0.36125)$$

$$\lambda_f^2 \sim IG(0.5, 0.125)$$

The priors for the longitudinal model parameter γ_t are show in Table 1.

Table 1: Prior parameters for longitudinal model parameter γ_t

	μ_γ	σ_γ^2
Week 1 to Week 12	0	1
Week 4 to Week 12	0	1
Week 8 to Week 12	0	1

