4.1 Virtual Subject Response Profiles

4.1.1 Final Endpoint Scenarios

We consider 6 scenarios for the final 12-week endpoint values. The null model assumes no dose-response. The other 4 scenarios (I-V), depicted in Figure 2, assume a dose-response all based on a sigmoidal model of different size and shape. Table 1 presents the respective parameter values underlying these scenarios. We evaluate these scenarios assuming the standard deviation of the final 12-week endpoint will be 0.95.

Trial Code: 000233

Table 1: Sigmoidal parameter values and their corresponding ED85 and MED of the different scenarios (note: dose runs from 0 to 5 units)

Scenario	α_2 (max effect)	α_3 (ED50)	α_4	ED85	MED
Null	0	-	-	-	-
I	-0.3	150	4	228	-
II	-0.4	200	4	297	263
III	-0.5	200	4	297	221
IV	-0.5	350	8	417	368
V	-0.6	300	8	368	300

Note : $\alpha_0=0$

[figure not shown]

Figure 2: Mean Dose-Response Scenarios

Trial Code: 000233

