$$\mu_d = \alpha_1 + \frac{(\alpha_2 - \alpha_1)d^{\alpha_4}}{d^{\alpha_4} + \alpha_3^{\alpha_4}}, \quad (2)$$

where  $d$  is the dose measured in 100  $\mu\text{g}$  (so  $d=0, 0.5, 1, 1.5, 2.5, 3.5$ , or  $5$ ), and the interpretation of the parameters are:  $\alpha_1$  is the placebo response for a subject with 2 nocturnal voids at baseline;  $\alpha_2$  is the maximum response for a subject with 2 nocturnal voids at baseline;  $\alpha_3$  is the dose ( $ED_{50}$ ) at which 50% of the maximum effect is obtained; and  $\alpha_4$  is the slope parameter. In the primary analysis of  $y_{4,i}$ , the model parameters  $\theta = (\beta, \alpha_1, \alpha_2, \alpha_3, \alpha_4, \sigma^2)$  are modelled with the prior distributions  $\beta \sim N(0, 10^2)$ ;  $\alpha_1 \sim N(-1, 3^2)$ ;  $\alpha_2 \sim N(-0.5, 2^2)$ ;  $\alpha_3 \sim N^+(2, 2^2)$ ;  $\alpha_4 \sim N^+(5, 3.5^2)$ ; and  $\sigma^2 \sim IG(0.5, 0.605)$ , where the notation  $N^+(\eta, \zeta^2)$  refers to a positive truncated normal distribution, and the  $IG(a, b)$  is the inverse gamma distribution.

Missing data due to drop out or insufficient Voiding Diary data at Visit 8 will be imputed using a longitudinal model applied to the observed data including all visits, corresponding to a missing-at-random assumption. The longitudinal model of  $y_{t,i}$  is modelled conditional on an individual parameter,  $\delta_i$ , modelling  $y_{t,i}$  as

$$y_{t,i} = e^{\xi_t} (\beta(x_{0,i} - 2) + \mu_d + \delta_i) + \varepsilon_{t,i} \quad (3)$$

where  $\xi_4=0$ . Bayesian analysis will be based on the same priors as in the primary analysis described above for the  $\beta$  and the  $\alpha$  parameters, while the remaining parameters are modelled with the priors:  $\xi_t \sim N(0, 1)$ ;  $\delta_i \sim N(0, \tau^2)$  with  $\tau^2 \sim IG(0.5, 0.36125)$ , and  $\varepsilon_{t,i} \sim N(0, \lambda_t^2)$  with  $\lambda_t^2 \sim IG(0.5, 0.125)$ .

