In addition to the illustrations of the therapeutic window specified in the protocol, illustrations of the therapeutic window will be produced using the estimated treatment contrast compared to placebo for the change from baseline-RT to lowest post-baseline measurement of serum sodium as the safety indicator. The inclusion of desmopressin in the plots illustrating the therapeutic window (“Corresponding efficacy and safety of desmopressin will be illustrated in a side panel for comparison.”) has been deleted to comply with “None of the primary, secondary or explorative analyses will include desmopressin.” (Section 10.1).

In the analyses of time to ‘confirmed’ hyponatraemia episodes, the time to event is defined as the time of confirmation in stead of the time to first measurement below the threshold to avoid conditioning on the future. The protocol states “The associated relative hazards of treatment and gender will be analysed using Cox proportional hazards model adjusting for baseline serum sodium and age (<65,  $\geq$ 65 years). Possible heterogeneity between the genders in the relative treatment hazards will be explored by the inclusion of a treatment-by-gender interaction term”. These analyses will not be performed since the trial is too small to perform Cox regression analyses of the occurrence of hyponatraemia events with 9 treatment groups and 2 covariates.

The adverse events tables presenting incidences of least 5% have been changed to presenting at incidences of at least 10% because it is expected that for several of the FE 201836 treatment groups, 20 subjects or less are allocated to the group.

According to [REDACTED], the interim analyses will deviate from the Appendix 2 in the protocol regarding the derivation of the allocation probabilities by the factor  $1/(n_d + 1)$  before the normalization to sum to 1.

Remaining changes are all considered clarifications of presentations specified in the protocol.

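### The SAP imputes missing 12-week averages with one time course shared by placebo and all FE 201836 doses, where protocol Appendix 2 fits control and FE 201836 separately; SAP 14 does not list the change, and the possible bias is small and conditional

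*SAP*

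**What the plan says.** SAP 10.2.1 defines the primary endpoint as the change in nocturnal voids averaged over all post-randomisation visits. Missing values of it "will be imputed using a longitudinal model applied to the observed data including all visits". Equation (3) multiplies the subject's mean by e^ξ_t, where ξ_t has no arm index, and uses one τ² and one λ_t² per visit. The list of sampled parameters contains a single ξ_1 to ξ_3 and a single λ_1² to λ_4². Sensitivity analysis 1 in SAP 10.2.2 accordingly reports one exp(ξ_1) to exp(ξ_3). SAP 10.1 excludes desmopressin, so this one course covers placebo and all FE 201836 doses.

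Protocol Appendix 2, section 2.2, says otherwise: "The control, active comparator, and 6 active doses of FE 201836 are modeled with separate model instances". It adds: "Each model instance will be fit using only the data from the arm(s) it corresponds to". Its section 2.5 imputes drop-outs from that model.

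Protocol 9.7.2.1 writes γ_t, τ² and λ_t² without an arm index, and refers to Appendix 2 for the handling of incomplete subjects.

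SAP 14 lists departures from the protocol, including one from Appendix 2 (an extra factor in the allocation probabilities). The imputation model is not among them. The section closes: "Remaining changes are all considered clarifications of presentations specified in the protocol".

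**The concern.** A shared e^ξ_t assumes that placebo and every dose have reached the same fraction of their final average change at Weeks 1, 4 and 8. An antidiuretic could act from the first nights while a placebo response accumulates, or the placebo response could come early and the drug effect later. In either case the fitted fraction lies between the two true ones. Final values imputed from early visits are then too small in one arm and too large in the other, even when drop-out is unrelated to outcome.

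The quantities exposed are the estimated 500 µg effect, the 0.3-void rule behind the MED, and the ED85. The choice of imputation model is also not a matter of presentation, which is how the last sentence of SAP 14 would classify it.

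**Working it through.** **Planning figures.** The plan gives no number for this bias. Its power figure serves to check the standard error used as a yardstick. Placebo receives 50 + 0.2 × 175 = 85 subjects. With 85 also assumed on 500 µg, SE = 0.95 × √(2/85) = 0.146. In Scenario III the effect at 500 µg is −0.5 × 500⁴/(500⁴ + 200⁴) = −0.4875. A two-sided 5% test then has 91.7% power, against 90.4% stated. For 60 to 120 subjects on 500 µg the range is 86.1% to 95.2%. The simulated figure is bracketed, not exactly reproduced, and nothing below depends on it.

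**Inputs from the documents**
- Drop-out: "Constant dropout rate of 15% during the randomised treatment period" (protocol 9.1), spread evenly over the 12 weeks.
- Variance: Appendix 2, section 4.1.1, proceeds "assuming the standard deviation of the final 12-week endpoint will be 0.95". The between-subject share is 0.90, so τ² = 0.90 × 0.9025 = 0.812.
- Planning time course: "Response fractions of 0.8142, 0.9328 and 0.9874 at Weeks 1, 4 and 8, respectively".
- Planning variances: "Variance fractions of 0.8481, 0.8329 and 0.8900 at Weeks 1, 4 and 8, respectively".
- Visit error, from Appendix 2, section 4.1.2: κ_t² = φ_t σ² − f_t² τ². For this to be non-negative, f_t cannot exceed √(φ_t/0.90), which is 0.971, 0.962 and 0.994 at Weeks 1, 4 and 8.

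**Assumptions.** The documents give neither a placebo change nor arm-specific courses. I took a placebo change of −1.0 (the centre of the α_1 prior), varied from −0.5 to −1.5, and the courses in the table.

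**Method.** Very large two-arm samples (placebo and 500 µg) were generated with the Appendix 2 formula. The model y_t = e^ξ_t(μ_d + δ_i) + error was fitted by maximum likelihood without the baseline covariate, once with shared ξ, τ and λ and once by arm. Missing y_4 was imputed and the contrast compared with that from complete data.

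| Placebo fractions (Weeks 1/4/8) | 500 µg fractions | Bias, shared | Bias, by arm | Shared bias / 0.146 |
|---|---|---|---|---|
| planning | planning | 0.001 | 0.001 | 0.00 |
| 0.65/0.80/0.92 | planning | −0.024 | −0.002 | −0.17 |
| 0.50/0.70/0.88 | 0.94/0.95/0.985 | −0.048 | 0.000 | −0.33 |
| 0.95/0.95/0.98 | planning | +0.009 | 0.000 | +0.06 |
| 0.97/0.96/0.99 | 0.65/0.80/0.92 | +0.040 | +0.003 | +0.27 |

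A negative sign exaggerates the drug effect. In the second row the shared Week 1 fraction is fitted at 0.763, between 0.65 and 0.8142. The placebo mean is then off by +0.014 and the 500 µg mean by −0.010, and −0.010 − 0.014 = −0.024.

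Against the 0.3-void margin, 0.009/0.3 = 3% and 0.048/0.3 = 16%. For placebo changes of −0.5 to −1.5, the second row runs from −0.012 to −0.035 and the third from −0.030 to −0.070. Spreading drop-out evenly over visits instead of time gives −0.020 and −0.045 for these two rows.

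**Low doses.** Appendix 2 puts all six FE 201836 doses in one instance. With a third arm added, a low dose that follows the placebo course, the shared model leaves that dose unbiased and the high dose off by about −0.022. Separate instances reduce the high-dose bias to between 0.002 and 0.012. They give the low dose a bias of about +0.016 to +0.018 for the second row's courses and +0.036 to +0.043 for the third's.

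**The case against.** The strongest reply is that the SAP follows the protocol's main text. A reader might infer from Appendix 2 that the SAP plainly contradicts the protocol, and the documents do not support that. Section 9.7.2.1 and the synopsis both write the time course without an arm index. However, the protocol calls its account of the model a brief background and sends the reader to Appendix 2 for the imputation, so the more specific text is the separate one. What stands is an unexplained choice between two protocol texts, which belongs in SAP 14.

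The planning profile was common to all arms, and under it the bias is zero. That is correct, but the simulations could not have tested the assumption. They set the placebo mean to 0, and any fraction of 0 is 0.

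A reader might also infer a large error per subject. Under another assumed set of courses and variances, placebo subjects seen only at Week 1 are imputed about 0.20 voids short. The arm-specific model leaves them about 0.14 short, so sharing adds only about 0.06, in 3/12 × 15% = 3.75% of the arm. In that calculation separate fits also left a contrast bias of −0.010, against −0.020 shared. The near-zero column in the table therefore owes something to generating the data from the form that was fitted.

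Finally, other analyses are planned: completers (SAP 10.2.2, item 5), a placebo-based MMRM (item 7), and an MMRM of the aggregated average with treatment-by-visit terms (SAP 10.3.4). These are useful partial checks. None repeats the primary analysis with arm-specific courses.

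**Conclusion.** The discrepancy between SAP equation (3) and Appendix 2 is in the text and is not disclosed. Its numerical consequence is conditional and small: roughly 0.01 to 0.05 voids in the 500 µg contrast at 15% drop-out and a placebo change of −1.0, of either sign, and up to 0.07 in the most extreme case run. It vanishes if the two courses match. The documents do not say whether they do, so the size rests on assumed time courses and an assumed placebo change.

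Two stronger conclusions should not be drawn. The first is that the stated 3.0% false-positive rate is undermined: an inert drug would be expected to follow the placebo course, where the bias is zero. The second is that arm-specific imputation removes bias at every dose: with all doses in one instance, it can shift near-ineffective low doses by about 0.02 to 0.04 voids. The point bears on the magnitude of the 500 µg effect and on MED and ED85.

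**What to change.** Preferred: index ξ_t, τ² and λ_t² in equation (3) by placebo versus FE 201836, as Appendix 2 specifies, and run the shared-course version as a sensitivity analysis. If the shared course stays primary, list it with a reason in SAP 14 and add the arm-specific version as a pre-specified sensitivity analysis before unblinding. Either way, report the MED under both versions, because the arm-specific version can move low doses.

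The cost is SAP wording, a few lines of code, and eight more nuisance parameters (three ξ, one τ², four λ²). Some precision is lost. I have not computed how much, but about 0.85 × 85 = 72 placebo completers would inform the placebo course. Imputing the missing visit values themselves, with treatment-by-visit means and an unstructured covariance, and then averaging them with the observed visits is an optional refinement that avoids the multiplicative form.

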4.1.2 Longitudinal Profile

We define a profile for generating the observed data at each earlier visit. Longitudinal data is simulated through the use of subject specific effects. For the i th subject, we simulate a subject effect

$$\delta_i \sim N(0, \tau_d).$$

Then for τ_d (one for each dose d), f_{dt} (one for each dose d and visit t), and ϕ_{dt} , with the constraint that all values are 1 for $t = T$ (the final endpoint time), visits are simulated by computing

$$\kappa_{dt}^2 = \phi_{dt}\sigma_d^2 - f_{dt}^2\tau_d^2$$

and then simulating visits

$$y_{it} \sim N([\theta_d + \delta_i]f_{dt}, \kappa_{dt}^2)$$

The purpose of this structure is to induce correlation through the random effect (interim visits all tend to be higher or lower than the group and arm mean depending on the random effect) while still maintaining a consistent interpretation of the final endpoint variance. Thus, marginally, we find

$$E[y_{it}] = f_{dt}\theta_d$$

and

$$V[y_{it}] = f_{dt}^2\tau_d^2 + \kappa_{dt}^2 = f_{dt}^2\tau_d^2 + \phi_{dt}\sigma_d^2 - f_{dt}^2\tau_d^2 = \phi_{dt}\sigma_d^2$$

so that the f_{dt} terms indicate the proportional value of the mean for the interim visit and the ϕ_{dt} terms indicate the fraction of proportional variance. As these modifiers are constrained to be 1 for the final visit, the interpretation of the final endpoint mean and variance are maintained (and thus the longitudinal model may be turned on and off and produce the same distribution for the final endpoint). We specify the fraction of overall variance that is due to inter-subject variance:

$$\omega_d = \tau_d^2/\sigma_d^2$$

The predictive value of the model occurs due to the correlation between time points, where

$$\text{Corr}(y_{it}, y_{it'}) = \frac{f_{dt}f_{dt'}\omega_d}{\sqrt{\phi_{dt}\phi_{dt'}}} \quad [t \neq t']$$

Trial Code: 000233

The parameter values for f_t and ϕ^2 are shown in Tables 2 and 3. These parameters are based on data observed from previous studies.

Table 2: Response Fraction (f) for the longitudinal profile

Week	f
1	0.8142
4	0.9328
8	0.9874
12	1.0000

Table 3: Fraction of the final variance (ϕ^2) for the longitudinal profile

Week	ϕ^2
1	0.8481
4	0.8329
8	0.8900
12	1.0000

We shall assume that the fraction of the overall variance due to inter-subject variance ω is 0.90

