## 10 Efficacy

### 10.1 General Considerations

For endpoints obtained from the Voiding Diary prior to a visit, the average of the endpoint across the 3 days will be interpreted as the cross-sectional observation of the endpoint in question at the specific visit, with the exception of the two endpoints, “Percentage of nights during the treatment period with at most one nocturnal void” and “Percentage of nights during the treatment period with complete response, i.e., with no nocturnal voids”.

If the baseline number of nocturnal voids is missing for a reason that can be considered to be missing completely at random (e.g., missing due to technical problems of the eDiary), the subject will not be included in any analyses that involve baseline measurements of nocturnal voids or other variables derived using baseline measurements of nocturnal voids.

The Bayesian dose-response analyses are conducted on aggregated averages, that is, outcomes averaged across preceding post-randomization visits. The posterior mean, median, and 95% credibility interval (2.5 and 97.5 percentiles of the posterior distribution) of quantities of interest as well as posterior probabilities of interest will be reported.

Frequentist inferences will rely on the appropriate choice of model and report p-values corresponding to the statistical test of the hypothesis of “no difference / no association” against the alternative of “any difference / any (linear) association”. The level of significance is set at 5% (two-sided).

Treatment comparison refers to the pair-wise comparison between each of the different doses of active treatment with FE 201836 and placebo. There are no planned adjustments for multiplicity when pair-wise testing the active treatment with different doses of FE 201836 versus placebo. Desmopressin is included as a benchmark treatment only. None of the primary, secondary or explorative analyses will include data from subjects treated with desmopressin. Explorative benchmarking analyses are further described in Section 10.5.

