### 10.2 Primary Efficacy Endpoint

#### 10.2.1 Primary Analysis

The primary endpoint is the aggregated average of change from baseline-RT in number of nocturnal voids after 12 weeks of treatment, that is, averaged across all post-randomization visits. The objectives of the primary analysis are to establish Proof-of-Concept of FE 201836 and to estimate the dose-response profile of FE 201836. The analyses will be performed on the ITT-RT analysis set.

The overall trial outcome is proof-of-concept evaluated by the posterior probability that 500 µg FE 201836 has superior efficacy as compared to placebo ( $Pr(\mu_{500} < \mu_{Plb}) > 97.5\%$ ) based on a Bayesian analysis of the dose-response profile at Week 12 for the ITT-RT analysis set not including the active comparator desmopressin.

The dose-response profile will be characterized by the posterior estimates of the mean dose-response at each dose,  $\mu_d$ , corresponding to two nocturnal voids at baseline and the mean dose-response contrast versus placebo,  $\Delta_d$ , with their associated 95% credibility intervals. The posterior probabilities  $Pr(\Delta_d < -0.3)$ ,  $Pr(\text{dose } d \text{ is MED})$ , and  $Pr(\text{dose } d \text{ is ED}_{85})$ , will be tabulated. The dose-response curve relative to placebo will also be presented graphically with its 95% credible interval in the plots illustrating the therapeutic window (Section 10.4). No multiplicity adjustment will be performed.

The dose-response profiles are determined using the following model: Let  $x_{t,i}$  denote the observed cross-sectional change from baseline-RT in nocturnal voids (averaged across the nights in the Voiding diary corresponding to the visit) and let  $y_{t,i}$  denote the aggregated average change from baseline for subject  $i$ , averaged across post-randomization visits up to time  $t$  (for visit windows see Section 3.1.5):

$$y_{t,i} = \frac{\sum_{k=1}^t x_{k,i}}{t}, \quad t = 1, 2, 3, 4,$$

where  $t$  denotes the nominal post-randomization time points reflecting Visits 5, 6, 7 and 8, corresponding to Weeks 1, 4, 8, and 12, respectively. The final endpoint,  $y_{4,i}$  is modelled as being an observation of

$$Y_{4,i} \sim N(\beta \cdot (x_{0,i} - 2) + \mu_d, \sigma^2), \quad (1)$$

where  $x_{0,i}$  is the baseline-RT number of nocturnal voids,  $\sigma^2$  is the error variance, and  $\mu_d$  describes the dose-response relationship.  $\mu_d$  is assumed to follow a four-parameter sigmoidal model:

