A total of 1000 imputations of the missing  $y_{4,i}$  will be performed. In the multiple imputation of the missing  $y_{4,i}$  for the primary analysis, a sample of size 1000 of the model parameters,  $\pi = (\xi_1, \xi_2, \xi_3, \beta, \alpha_1, \alpha_2, \alpha_3, \alpha_4, \delta_i \ (i=1, \dots, 300), \lambda_1^2, \lambda_2^2, \lambda_3^2, \lambda_4^2)$ , is first sampled from the posterior for the Bayesian analysis of the longitudinal model, using the seed=2720, a burn-in of 10 000 and a thinning factor of 50. Then for each set of model parameters,  $\pi_s$ , the imputed value of a missing  $y_{4,i}$  is obtained by adding a normally distributed error,  $\varepsilon_{4,i,s}$ , with seed=152 to the conditional mean of  $y_{4,i}$  (conditional on  $\delta_{i,s}$ ), giving a single imputation,  $y_{4,i,s}$ , thereby capturing all the variability in each imputed  $y_{4,i,s}$ .

For each of the imputed data sets, the Bayesian analysis of the (possibly imputed)  $y_{4,i}$  will be performed with a seed=10000+s using a burn-in of 10 000, and a single set of the model parameters  $\theta_s$  is obtained as number 50+s after the burn-in of the generated posterior values of  $\theta$ . The set  $\{\theta_s; s=1, \dots, 1000\}$  will be used to derive the  $\mu_d$  and  $\Delta_d$  with 95% credibility intervals and the posterior probabilities,  $Pr(\Delta_d < -0.3)$ ,  $Pr(\text{dose } d \text{ is MED})$ , and  $Pr(\text{dose } d \text{ is ED}_{85})$ .

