### 10.2.2 Sensitivity Analyses

The following sensitivity analyses will be conducted:

1. The mean, the median, and the 95% credibility intervals for  $\mu_d$ ,  $\Delta_d$ ,  $\exp(\xi_1)$ ,  $\exp(\xi_2)$ , and  $\exp(\xi_3)$ ; as well as the posterior probabilities,  $Pr(\Delta_d < -0.3)$ ,  $Pr(\text{dose } d \text{ is MED})$ , and  $Pr(\text{dose } d \text{ is ED}_{85})$ , will be presented for the longitudinal analysis used in the imputation of  $y_{4,i}$ .
2. The primary-analysis approach according to the planned treatment allocation will be carried out on the PP analysis set.
3. The primary-analysis approach according to the planned treatment allocation will be carried out on the ITT-RT analysis set, replacing  $\mu_d$  by  $\alpha_1$  in the conditional mean of missing  $y_{4,i}$  when imputing from the longitudinal model, that is, using a Missing Not At Random (MNAR) placebo model for the imputation of subjects who drop out.
4. The primary analysis according to the planned treatment allocation will be carried out on the ITT-RT analysis set using priors with twice as large scale parameters (standard deviations for normal distributions) than used for the primary analysis.
5. A Bayesian analysis will be performed for the observed value at Week 12 for completers, using a seed=10 000 and the same burn-in and thinning factor as specified for the longitudinal analysis, obtaining a final posterior sample size equal to the posterior sample size obtained in the primary analysis.

6. The primary-analysis approach but using the actual treatment allocation will be carried out on the Safety-RT analysis sets.

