## 14 Deviations From the Trial Protocol

A Full Analysis Set was defined in the protocol. However, none of the analyses specified in the trial protocol were based on the Full Analysis Set, so no Full Analysis Set has been defined in this SAP.

$Pr(\mu_d < \mu_{PLb})$  will be presented only for the 500 µg FE 201836 dose (Proof of Concept) since all doses will have the same probability because of the monotone dose-response curve parameterization; and  $Pr(\mu_d = \mu_{MAX})$  will not be displayed since it always equals 1 for the 500 µg dose, and probabilistically almost surely (that is, with probability 1) equals 0 for all other doses, again because of the monotone dose-response curve parameterization.

For some subjects, the baseline voiding diary is missing due to technical problems in the beginning of the study. The change from baseline in voiding data are considered missing completely at random for these subjects, and the subjects are not included in any analyses involving baseline measurements of voiding data.

Two sensitivity analyses have been added:

- Estimates of all quantities of interest based on the Bayesian analysis of the longitudinal model will be presented.
- A Bayesian analysis of the primary outcome with imputation using the level corresponding to placebo for drop-out.

The first sensitivity analysis presents the result for the model used for imputation. The second analysis is the Bayesian equivalent to the frequentist approach specified in the trial protocol based on a mixed model for repeated measurement (repeated-measurements ANCOVA) using MNAR placebo-based pattern mixture model.

Linear trend estimates have been added to the above mentioned protocol-specified frequentist approach as supplements to the description of the association with dose in case there are difficulties with the convergence for the primary analysis or very large uncertainties on the estimated  $\alpha$  parameters.

A secondary analysis of aggregated average change from baseline in nocturnal urine volume has been added. This outcome variable was added to comply with the Bayesian analysis mentioned in Table 9-4 in the trial protocol.

The ITT-RT data set will be used for all secondary analyses as stated in the protocol; but only observed data will be used. This is considered a clarification of the protocol.

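### The 97.5% proof-of-concept verdict rests on 1,000 posterior draws, with an unreported Monte Carlo SE of 0.49 points; ten thinned draws per chain would reduce it with no rise in total iterations

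*SAP*

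**What the plan says.** SAP 10.2.1 sets the decision rule: "The overall trial outcome is proof-of-concept evaluated by the posterior probability that" 500 µg is superior to placebo, with success if that probability exceeds 97.5%.

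The computation follows in the same section. "A total of 1000 imputations of the missing" final values is planned, all drawn from one longitudinal-model chain (seed 2720, burn-in 10,000, thinning 50). Each completed data set s then gets its own chain (seed 10000+s, burn-in 10,000), "and a single set of the model parameters" is kept from it, namely draw 50+s after burn-in. The resulting 1,000 sets supply μd, Δd, their 95% credibility intervals, and the MED and ED85 probabilities.

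The list of derived quantities does not name Pr(μ500 < μPlb). Section 14 says it will be shown for 500 µg only, "since all doses will have the same probability because of the monotone dose-response curve parameterization". Section 10.1 defines the reported interval as the "95% credibility interval (2.5 and 97.5 percentiles of the posterior distribution) of quantities of interest".

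Sensitivity analysis 5 in section 10.2.2 is run on completers, "obtaining a final posterior sample size equal to the posterior sample size obtained in the primary analysis". Neither document gives a Monte Carlo error, or a rule for a result close to the threshold.

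**The concern.** A yes/no trial outcome is read from a simulated proportion. With 1,000 draws, that proportion carries sampling noise that has nothing to do with the trial data. Each chain spends 10,000 iterations on burn-in and then contributes one draw, so the noise is larger than the computing effort requires. If the true posterior probability lies close to 97.5%, the declared outcome depends partly on which seeds were written into the SAP. Fixing the seeds makes the answer repeatable, but it does not make it less dependent on them. The MED and ED85 probabilities and the credibility limits come from the same 1,000 sets and carry the same kind of noise.

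**Working it through.** **1. Which draws decide the trial.** Section 10.2.1 reports the dose-response "corresponding to two nocturnal voids at baseline and the mean dose-response contrast versus placebo", Δd. Hence Pr(μ500 < μPlb) = Pr(Δ500 < 0). With percentile limits, an upper 95% limit for Δ500 below 0 is in effect the same decision. No other primary posterior sample is defined, so the 1,000 sets are the only source. Exceeding 97.5% needs at least 976 of 1,000 draws, because 975/1,000 is exactly 97.5%.

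**2. Monte Carlo SE now.** √(0.975 × 0.025 / 1000) = 0.00494, or 0.49 points.

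**3. Chance of a pass at a given true posterior probability p**, P(Bin(1000, p) ≥ 976):

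| True p | Passes | Fails |
|---|---|---|
| 96.5% | 3.0% | 97.0% |
| 97.0% | 15.3% | 84.7% |
| 98.0% | 84.5% | 15.5% |
| 98.5% | 98.9% | 1.1% |

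**4. How often this changes a verdict.** Take z ~ N(m, 1), true posterior probability Φ(z), and m = 1.96 + Φ⁻¹(success rate), using the success rates in SAP Table 2. This treats the design as a single look, without futility stopping or baseline adjustment. The 1,000-draw verdict is opposite to the exact one in 0.39% of trials if the null success rate is 2.5%, 0.46% at the plan's 3.0%, 1.2% in Scenario III and 2.7% in Scenario I. Errors in the two directions nearly cancel: power moves from 90.4% to 90.2% (III) and from 52.1% to 51.8% (I).

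**5. Share of information that is imputed.** Draws from one chain share an imputed data set, so ten of them are not worth ten independent draws. Protocol Appendix 2, section 4.1.2, supplies the inputs: response fractions 0.8142, 0.9328 and 0.9874; variance fractions 0.8481, 0.8329 and 0.8900; and "We shall assume that the fraction of the overall variance due to inter-subject variance" is 0.90. Correlations with the final value are 0.8142 × 0.90/√0.8481 = 0.80, then 0.92 and 0.94. The unexplained shares 1 − r² are 0.367, 0.154 and 0.113. With 15% dropout spread equally over four intervals, (0.15/4) × (1 + 0.367 + 0.154 + 0.113) = 0.061. I use f = 5% to 15%. The upper value is an assumption, corresponding to intermediate visits that carry no information.

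**6. SE with ten draws per chain.** SE = √((B + W/10)/1000). B and W are the between- and within-imputation variances of the success indicator, from a bivariate normal with correlation f, and B + W = 0.975 × 0.025 = 0.024375.
- f = 5%: B = 0.000188, W = 0.02419, SE 0.161 points
- f = 10%: B = 0.000412, W = 0.02396, SE 0.168 points
- f = 15%: B = 0.000676, W = 0.02370, SE 0.175 points

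The gain is 0.494/0.161 = 3.1-fold to 0.494/0.175 = 2.8-fold, provided draws 50 iterations apart are nearly independent. If their correlation is ρ, the 10 is replaced by 10/(1 + 2Σ(1 − k/10)ρᵏ), k = 1 to 9. This is 5.8 at ρ = 0.3 (SE about 0.21), 3.8 at 0.5 (about 0.26) and 1.4 at 0.9 (0.42). The ρ values are assumptions.

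Under near-independence, a true 97.0% passes about 0.2% to 0.5% of the time and a true 98.0% fails less than 0.1%. Opposite verdicts fall to 0.13% to 0.16% (null), 0.38% to 0.41% (III) and 0.88% to 0.95% (I). For a MED or ED85 probability near 50%, the SE falls from √(0.25/1000) = 1.6 points to about 0.6 to 0.7.

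**7. Iterations.** Now: the sum over s of (10,000 + 50 + s) = 10,550,500. Proposed: 1,000 × 10,500 = 10,500,000. Of the 1,000 chains, 449 currently stop before post-burn-in iteration 500 and would gain 101,025 iterations in all; 550 run past it and would lose 151,525. Net: 101,025 − 151,525 = −50,500.

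**The case against.** The strongest reply is that no error has been shown. The procedure draws validly from the posterior. Seeds, burn-in and draw index are fixed in advance, so nobody can re-run until the answer suits, and average error rates hardly change. All of that stands. A reader might infer from the 0.49-point SE that the false-positive rate is inflated or that the analysis is invalid. Step 4 does not support this.

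A second reply is that the plan already tolerates noise of this size: its 3.0% false-positive rate comes from 1,000 simulated trials, with an SE of √(0.03 × 0.97/1000) = 0.54 points. That is true, but that noise blurs knowledge of the design's error rate. It does not touch the verdict on the actual trial.

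Third, a threefold gain cannot be promised. The SAP states thinning of 50 for the longitudinal chain only and gives no autocorrelation for the final model. Section 14 itself allows for convergence difficulties or very uncertain α parameters. One indicative sampler run on a single simulated data set gave a lag-50 autocorrelation of about 0.09 for Δ500, but the sampler was assumed. The gain must stay conditional. The same applies to cost: only the total does not rise, and keeping every chain at its present length while extending the short ones would add 101,025/10,550,500 = 0.96%.

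Finally, sensitivity analyses 1 and 4 give related estimates, so a borderline result would not be read alone. They use a different model or different priors, however, and do not measure Monte Carlo error.

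**Conclusion.** The point holds as an optional gain in precision, at the lowest severity. The primary decision is, by inference, taken on 1,000 draws with an SE of 0.49 points at the threshold. It matters only when the true posterior probability lies within about 1 point of 97.5%. Overall, about 0.4% of trials under the null and 1.2% to 2.7% in Scenarios III and I would get the opposite verdict, on a single-look approximation. The documents do not support a stronger reading, such as an invalid analysis, an inflated error rate, or a seed open to choice after the data are seen. The present SE and pass rates are straightforward binomial results. The size of the improvement is less certain: it rests on near-independence at lag 50 and on an imputed share of 5% to 15%. Missing Visit 8 diaries beyond the assumed dropout would raise that share.

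**What to change.** Before unblinding, amend SAP 10.2.1 in two or three sentences:

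- In every imputed-data chain, replace the single draw 50+s with the draws at iterations 50, 100, ..., 500 after burn-in.
- State that Pr(μ500 < μPlb), the MED and ED85 probabilities and all credibility limits use the pooled 10,000 draws.
- Check and report the lag-50 autocorrelation in these chains.
- Report the Monte Carlo SE of Pr(μ500 < μPlb) as the SD of the 1,000 per-imputation proportions divided by √1000. This allows for correlation within a chain, but assumes that the 1,000 imputations are nearly independent, although all come from one longitudinal chain thinned at 50. Batch means over s avoid that assumption.
- In 10.2.2, give sensitivity analysis 5 its own posterior sample size, because it is now tied to that of the primary analysis.

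Total computing does not increase. No rule for extending the run near the threshold is needed.
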